Pre-Specified Study Protocol and Statistical Analysis Plan

Original Project Title: Comparing the Effectiveness of Fatigue Management Programs for

People with MS

Version date of document: November 01, 2019

Clinical Trial Registration: clinicaltrials.gov #NCT03550170

Funding: This work was supported through a Patient-Centered Outcomes Research

Institute (PCORI) Project Program Award (MS-1610-37015). All statements in this report,

including its findings and conclusions, are solely those of the authors and do not necessarily

represent the views of the Patient-Centered Outcomes Research Institute (PCORI), its Board of

Governors or Methodology Committee.

Method and Analysis

Study Design

We are conducting a randomized clinical trial to directly compare three delivery formats of the *Managing Fatigue* intervention. We are using a pragmatic design approach in which 582 participants with MS are being recruited and randomized to teleconference, internet, or in-person versions of the intervention led by a licensed OT. All versions contain the same intervention content but are presented in ways most appropriate to the delivery format. Our goal is to recruit a diverse research sample to examine the effectiveness of each delivery format on different subgroups of participants (i.e., disease, demographic, and psychosocial characteristics). Outcomes are being measured at baseline, two months, three months, and six months. To help facilitate recruitment, the study is being branded as REFRESH (**RE**ducing **F**atigue and **R**estoring **E**nergy to **S**upport **H**ealth).

Sample Size and Inferiority Margin

A sample size of 582 participants is needed to achieve a power of 0.90 for testing the hypothesis and conducting the moderation analyses. Based on previous studies and to err on the side of being conservative, we assumed an attrition rate of 35%, a standardized mean difference of 0.3, a correlation of 0.45 (rho), and a two-sided alpha level of 0.05. An interaction-to-overall effects ratio estimated the extra number of participants needed to examine interactions between delivery formats and participants' baseline characteristics. The prespecified inferiority margin is ten points, which is based on triangulating anchor-based and distribution-based methods to calculate the minimally important difference (MID) on the Fatigue Impact Scale (FIS), and is consistent with a standardized mean difference of 0.3.3-5

Recruitment and Eligibility

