Each participant will be randomized to receive one of the three interventions. Participants are randomized only after availability is confirmed for each delivery format, baseline data collection is complete, and there are enough participants within a specific geographic region (18 to 30 participants) to conduct the group sessions. Permuted block randomization is being implemented. A statistician, who is not involved with data collection or participant interactions, developed a random number table using a 1:1:1 allocation ratio in blocks of six. The statistician directly imported the table into the Research Electronic Data Capture (REDCap)⁸ system to conceal group assignment. REDCap reveals group assignment only after all baseline data are collected and verified by the project manager. Participants are permitted to switch group assignment only when we are unable to provide services (e.g., an OT becomes sick and is no longer able to deliver services or a participant is unable to use a computer).

Masking

As in most behavioral and rehabilitation interventions, direct interaction between participants and OTs is required, making complete masking impossible. To mitigate bias, each OT is delivering only one intervention format, i.e., teleconference, internet, or one-to-one. Data collectors are being masked to group assignment to minimize any biases in baseline or follow-up data collection. We are also measuring the expectations of benefits for each delivery format and conducting sensitivity analyses on measures of treatment fidelity. The study is being described to

participants as a comparison of three courses that could all be equally beneficial for reducing the impact of fatigue.

Intervention Procedures

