notify the research office immediately if they suspect an adverse event. The participant's physician is informed when additional services are needed for the treatment of an adverse event. Because it is unlikely that these adverse events will be related to the study protocol, an independent Data and Safety Monitoring Board is not being utilized. If a serious adverse event is related to the protocol, the Institutional Review Board and study sponsor will be notified immediately. Quality control checks (e.g., data generation and attrition rate) will occur throughout the study (i.e., every few months) by the statistician not involved in data collection or delivery of the intervention. Concerns about adverse events or quality control checks will be discussed in the monthly team meetings and conveyed to other stakeholder groups convened during the study, including people with MS.

Data will be downloaded from REDCap into a statistical software program. Linear mixed effects model will serve as the primary analysis tool for examining the differential effects of the intervention delivery format on outcomes. The models will include the group assignment variable, time, and interaction of time and group, as well as the subject-specific random intercept and slope for accounting for individual heterogeneity. Using the fitted model, the trajectory of outcomes will be plotted over the study period. Direct estimates of the treatment effect at specific times will be derived by specifying the least squares means for the Treatment × Time interaction. Noninferiority will be established with a 95% confidence interval (CI) using the prespecified margin of inferiority at each time point, which is set at ten points on the total composite score of the FIS. The prespecified inferiority margin for the Multiple Sclerosis Impact Scale is set at eight points for the physical function subscale and six points for the psychological function subscale. These margins are based on anchored-based methods calculated from previous studies.²⁵ ²⁶

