A series of sensitivity analyses are planned to explore how various assumptions and potential confounders might influence the results. Four pre-specified sensitivity analyses are planned: (1) significant differences in time-varying factors between groups after randomization (e.g., exacerbations, changes in medications, or changes in health and wellness services), (2) assumptions of missing data, (3) differences in prespecified margins, and (4) treatment fidelity measures (e.g., attendance, quizzes, and experience of OT). We plan to examine these factors by comparing adjusted to non-adjusted models. Significant differences in time-varying factors between groups after randomization will be entered into the model as covariates during hypothesis testing. We will examine whether any differences exist in results based on how missing data are treated (e.g., missing at random versus missing not at random). We will also use prespecified margins of 4.8 (i.e., standard error of measurement), 15.5 (the mean of 12 anchoredbased MIDs), and 20 (upper limit of the triangulated anchored and distribution-based MIDs). Last, we will assess whether measures of treatment fidelity, such as OT experience and participants' understanding of material, influence outcomes as well as whether differences exist in the per-protocol analysis when participants who provide complete data and attend all six intervention sessions (compared to four and five of the six sessions) are only included in the analysis.

Public and Patient Involvement

Stakeholder groups comprising individuals with MS, policy advocates, insurance representatives, clinicians, and researchers on the project are informing all aspects of the study. This includes drafting and reviewing recruitment and intervention material, branding of the study, selecting which delivery formats to examine, assessing and finding both the ease and

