The authors would like to thank the participants for their time. We also would like to thank [name], [name], [name], [name], [name], and [name] for assistance with intervention refinement and/or development as well as ongoing recruitment, enrollment, data collection, and/or intervention delivery.

Conflict of Interest

[name] has financial relationships with pharmaceutical and devices companies outside the submitted work. The other authors declare that they have no potential or actual conflict of interest pertaining to this research study.

Funding

This work was supported through a Patient-Centered Outcomes Research Institute (PCORI) Project Program Award (MS-1610-37015). All statements in this report, including its findings and conclusions, are solely those of the authors and do not necessarily represent the views of the Patient-Centered Outcomes Research Institute (PCORI), its Board of Governors or Methodology Committee.

Table 1. Schedule of enrolment, interventions, and assessments

Table 1. Schedule of enrolment, interventions, and asses	STUDY PERIOD					
	Enrolment	Allocation	Interventions	Post	t-allo	cation
TIMEPOINT**	-t ₁	0		t ₁	t_2	t ₃
ENROLMENT:			1			
Eligibility screen	X					
Informed consent	X					
In-person assessment	X					
Return baseline questionnaire packet	X					
Allocation		X				
MANAGING FATIGUE INTERVENTION:			I			
One-to-one, in-person			+			
Internet			•			
Teleconference			•			
PRIMARY OUTCOME:			 			
Fatigue Impact Scale ²⁰	X			X	X	X
SECONDARY OUTCOMES:	71			71	71	71
Multiple Sclerosis Impact Scale ²¹	X			X	X	X
Community Participation Indicators ²² 27	X			X	X	X
MODERATORS	21			21	71	71
Multiple Sclerosis Functional Composite ³¹	X					
Medical Term Recognition Test ³²	X					
Neuro QOL – Anxiety ³³	X			X	X	X
Neuro QOL – Sleep ³³	X			X	X	X
Patient Health Questionnaire–8 ³⁴	X			X	X	X
Patient Activation Measure ³⁵	X			71	71	X
Craig Hospital Inventory of Environmental Factors ³⁶	X					- 21
Demographics (i.e., urban/rural and race)	X					
Self-report Comorbidity Questionnaire ³⁷	X					
Modified Social Support Survey ³⁸	X					X
MEDIATORS			I		 	
Energy Conservation Strategies Survey ¹⁹	X			X	X	X
Self-Efficacy for Performing Energy Conservation						
Strategies Assessment ¹⁸	X			X	X	X
Chronic Disease Self-management Scale ³⁹	X			X	X	X
COVARIATES & POSSIBLE CONFOUNDERS						
Sociodemographic (e.g., age, gender, income,	37					

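### The primary model does not use baseline FIS to sharpen the visit contrasts, which gives up about 14–18% of their variance at rho 0.45 with 35% attrition (less at month 6 if slopes vary)

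*Combined protocol and SAP*

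**What the plan says.** Data Management and Analysis lists the terms of the primary model: "The models will include the group assignment variable, time, and interaction of time and group, as well as the subject-specific random intercept and slope". The format effect is then read off visit by visit: "Direct estimates of the treatment effect at specific times will be derived by specifying the least squares means" for the interaction of treatment with time. Noninferiority is judged by a 95% CI against 10 FIS points at each time point.

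The only covariates named for hypothesis testing come later in the same section, under the sensitivity analyses, and they arise after allocation: "Significant differences in time-varying factors between groups after randomization will be entered into the model as covariates during hypothesis testing". Fidelity measures are also to be examined. Table 1 has a block for covariates and possible confounders, and baseline FIS is not in it.

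Table 1 does show the FIS collected at enrolment and at 2, 3 and 6 months. Randomization and Allocation Concealment adds: "REDCap reveals group assignment only after all baseline data are collected and verified by the project manager". Under Sample Size and Inferiority Margin, the planning inputs are: "we assumed an attrition rate of 35%, a standardized mean difference of 0.3, a correlation of 0.45 (rho". The plan does not say which correlation rho is.

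**The concern.** A free group term together with group × time lets each arm have its own baseline mean. Because baseline FIS precedes allocation, the arms share one baseline mean by design, and the model does not use that fact.

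The random intercept does not fill the gap. With categorical time and complete data, the least-squares-mean difference at a visit is simply the raw difference in means there, and baseline adds no precision. With dropout, earlier rows help to recover missing visits, but that is only part of what baseline can give.

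This is lost efficiency, not bias. Randomization makes the unadjusted contrast valid, and its CI already allows for chance imbalance at baseline. What is at stake is the width of an interval whose bound decides noninferiority.

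A separate gap is that the form of time is not stated. Least-squares means at specific times suggest categorical time, while a random slope and a plotted trajectory could be read as linear time. The two give different visit estimates.

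**Working it through.** **Inputs from the plan.** 582 participants at 1:1:1, so 194 per arm; visits at 0, 2, 3 and 6 months; attrition 35%; rho 0.45; two-sided alpha 0.05; margin 10 points, said to match a standardized difference of 0.3, so SD = 10/0.3 = 33.3.

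**Assumptions.** Rho is the baseline-to-follow-up FIS correlation; time is categorical; the contrast is the difference in level at a visit; the true difference is 0. Dropout is either all before month 2 (early) or one third before each follow-up visit (progressive: 88.3%, 76.7% and 65% retained).

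**The plan's own figure.** 582 cannot be uniquely reproduced, because the contrast, the correlation structure, the dropout pattern and the interaction ratio are not given. A plain two-mean calculation gives 2 × (1.960 + 1.282)²/0.3² = 234 per arm, or 702 in total (1,080 after dividing by 0.65). Averaging the three follow-up visits with staged attrition gives 573–588 under one approximation and 546–561 under another. The comparison below does not depend on how 582 was reached.

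**Complete data** (variance of a pairwise contrast, in units of σ²/n):
- free baseline means: 2
- common baseline mean: 2(1 − ρ²) = 2 × 0.7975 = 1.595
- saving: ρ² = 20% at 0.45 (9% at 0.30, 25% at 0.50, 36% at 0.60)

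**Early dropout, compound symmetry** (fraction 0.65 retained):
- free: 2[(1 − ρ²)/0.65 + ρ²] = 2[1.2269 + 0.2025] = 2.859
- common: 2(1 − ρ²)/0.65 = 2.454
- ratio: 2.454/2.859 = 0.858, a saving of 14.2% at every visit

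The raw-mean variance would be 2/0.65 = 3.077, so the planned model has already recovered 1 − 2.859/3.077 = 7%. The 14.2% is on top of that. Over both dropout patterns and all visits this existing recovery is about 2–10%.

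**Progressive dropout, compound symmetry, rho 0.45** (generalized least squares):

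| Visit | Free | Common | Ratio | Saving |
|---|---|---|---|---|
| Month 2 | 2.211 | 1.806 | 0.817 | 18.3% |
| Month 3 | 2.459 | 2.054 | 0.835 | 16.5% |
| Month 6 | 2.777 | 2.372 | 0.854 | 14.6% |

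The absolute gain is 2ρ² = 0.405 in every row. A 4,000-replicate simulation gave savings of 18.9%, 16.2% and 13.0%, consistent within Monte Carlo error. At other values of rho, the savings across visits and both dropout patterns are 6–8% (0.30) and 27–33% (0.60).

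**Month 6 in FIS points.** SE = 33.3 × √(variance/194); power = Φ(10/SE − 1.96).
- early: SE 4.05 → 3.75; power 0.70 → 0.76
- progressive: SE 3.99 → 3.69; power 0.71 → 0.77

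The CI half-width falls from 7.8–7.9 to 7.2–7.3 points.

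**Random slopes.** The plan gives no slope variance. With an assumed slope SD of 2–4 points per month, intercept–slope correlation of −0.3 to 0, and the baseline-to-month-2 correlation held at 0.45, the baseline-to-month-6 correlation is 0.31–0.43. The saving is then 14–18% at month 2, 12–16% at month 3 and 6–13% at month 6. An intercept–slope correlation of +0.3 gives 13–15% at month 6.

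**Equivalent sample size at month 6.** 582 × (1/ratio − 1): 40 participants at ratio 0.936 (slope SD 4, correlation −0.3) and about 100 at 0.854.

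**If time is linear.** Take arm differences of 0, 10, 10, 10 at t = 0, 2, 3, 6. Mean t is 2.75 and mean difference 7.5, so the slope is 27.5/18.75 = 1.467 and the intercept 7.5 − 1.467 × 2.75 = 3.47. Fitted differences are 6.4, 7.9 and 12.3 at months 2, 3 and 6. With 35% dropout and compound symmetry at 0.45 they are 5.6–6.2, 7.1–7.8 and 11.8–12.8.

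**The case against.** The strongest reply is that a mixed model with baseline in the outcome vector is a standard, valid analysis, that nothing in the plan contradicts itself, and that the gain is modest: about 0.6 point of CI half-width and 6–7 percentage points of power. That is fair, and it is why this is an improvement the plan should make rather than an invalidity.

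The size does depend on choices the plan does not state.

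- **Covariance.** Compound symmetry means no slope variance, yet the plan specifies a random slope. The month-6 saving is then lower: 6–13% over the slopes above, and about 4–14% over a wider assumed range. If rho were meant as an AR(1) correlation by visit, the saving would be about 3% at month 3 and under 1% at month 6. AR(1) is not the covariance that a random intercept and slope implies, and adjustment would still cost essentially nothing.
- **Contrast.** If change from baseline is intended, the gain is larger, about 20–25% under attrition.
- **Clustering.** Two formats run in groups of five to ten. With an assumed intraclass correlation of 0.05, the 14–18% becomes roughly 11–16% for a group format against one-to-one.
- **Power.** The figures are for one contrast at one visit, and the plan does not say which contrast its 0.90 refers to.
- **Time.** The linear-time distortion is conditional, since the plan does not say that time is linear. It is a reason to state the coding and does not support the efficiency claim.

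These points move the size of the gain. None supplies the missing baseline adjustment.

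**Conclusion.** The concern holds. The planned model neither conditions on baseline FIS nor sets a common baseline mean, so its visit contrasts carry avoidable variance. With rho 0.45 read as the baseline-to-follow-up correlation, categorical time, a level contrast and 35% attrition, the avoidable part is 14–18% under compound symmetry, and 6–13% at month 6 under the assumed random slopes. Over these covariances the month-6 gain is worth roughly 40–100 extra randomized participants.

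The adjustment does not by itself bring a single-visit contrast to 0.90. Under compound symmetry with 35% attrition, adjusted power is 0.76–0.87 across visits. Confidence in the omission is high; confidence in the exact size is medium, because rho, the covariance, the contrast and the form of time are all left open.

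**What to change.** In Data Management and Analysis:

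1. State that time is categorical (0, 2, 3 and 6 months).
2. Pre-specify one common baseline mean for the three randomized arms, with group effects at each post-baseline visit. Alternatively, enter baseline FIS and baseline × time as covariates, with the three post-baseline visits as outcomes.
3. Derive the noninferiority CIs from that model, and do the same for the two Multiple Sclerosis Impact Scale subscales.
4. Under Sample Size and Inferiority Margin, say what rho refers to.

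The cost is SAP wording: baseline FIS is already collected from everyone before randomization, and no assumption beyond randomization is added. Randomization began in March 2019, so the change should be dated and made before outcome data are compared by arm. If it counts as a protocol modification, the plan requires submission to the IRB first.

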The purpose of the moderator analysis will be to examine the consistency of the intervention's effect across the following subgroups: (1) disability status (i.e., people with moderate to severe disabilities vs. people with mild impairments, (2) race (i.e., Hispanic and non-whites vs. non-Hispanic whites, (3) environment (i.e., people living in rural areas vs. urban areas), and (4) psychosocial characteristics (i.e., people experiencing societal barriers, depression, low health literacy, low social support, and/or low patient activation vs. people without these characteristics). This analysis will involve adding an additional interaction term of group × time × characteristic and the two-way interaction term of time × characteristic and group × characteristic using the mixed effects model that will be used to detect the main treatment effects on fatigue impact.

The purpose of the mediator analysis will be to examine whether changes in self-efficacy and fatigue self-management behaviors influence the relationship between the interventions and outcomes. Significant changes across time in self-efficacy and fatigue self-management behaviors will be evaluated using the proposed mixed effects analysis. Following Hayes et al.,²⁸ the mediation analysis will involve a series of regression analyses to quantify mediation effects using bias-corrected bootstrapped 95% CI.

We will conduct analyses using both intention-to-treat and per-protocol principles. When using intention-to-treat principles, the treatment of missing values will depend on the type of missingness. In the case of missing at random, the proposed mixed effects models should be sufficient. In the case of missing not at random or non-ignorable, a Bayesian method to jointly model response data and missing data will be applied. When using per-protocol principles, participants who provide complete data and attend four or more intervention sessions will be included in the analysis.

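### Disability and psychosocial moderators are described only as two-category subgroups without cut-points, although scored baseline instruments are listed; testing the scores would generally be more powerful

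*Combined protocol and SAP*

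**What the plan says.** The moderator paragraph of Data Management and Analysis names four kinds of subgroup. Disability is contrasted as "people with moderate to severe disabilities vs. people with mild impairments". Race and rural/urban residence are categories by nature. The psychosocial item joins societal barriers, depression, low health literacy, low social support and low patient activation with an *and/or*, against people without these traits. The test adds the three-way term of group, time and characteristic, with the matching two-way terms, to the main mixed model. The paragraph does not say how the characteristic is coded, and it gives no cut-point.

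Under Moderators, Table 1 lists baseline instruments that correspond to these traits: the "Multiple Sclerosis Functional Composite", the PHQ-8, the Medical Term Recognition Test, the Modified Social Support Survey, the Patient Activation Measure and the Craig Hospital Inventory of Environmental Factors.

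Moderation also helps to justify the sample size. Sample Size and Inferiority Margin states: "A sample size of 582 participants is needed to achieve a power of 0.90 for testing the hypothesis and conducting the moderation analyses". It adds: "An interaction-to-overall effects ratio estimated the extra number of participants needed to examine interactions". The value of that ratio is not given.

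**The concern.** Study Design makes differences between subgroups a goal of the trial, and participants were added for the interaction tests. Cutting a score in two discards the variation within each half, so it gives back some of the power those participants were meant to buy.

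Without stated cut-points, the subgroups can also be formed after the data are seen, and the result may depend on where the line falls. The plan does fix numbers elsewhere: a Fatigue Severity score of at least 4 for entry, four or more sessions for the per-protocol set, and alternative margins of 4.8, 15.5 and 20. The *and/or* wording leaves a second choice open, because it could mean one pooled psychosocial category or five separate moderators.

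**Working it through.** **1. The plan's own figure.** The stated inputs are N = 582 allocated 1:1:1, power 0.90, attrition 35%, standardized difference 0.3, rho 0.45 and "a two-sided alpha level of 0.05". The size of the interaction ratio and the contrast that was powered are missing, so 582 cannot be reproduced in full. Comparing two arms:

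- One time point: n per arm = 2(1.96 + 1.2816)²/0.3² = 233.5, so 234. Three arms make 702, and 702/0.65 = 1,080.
- Mean of three follow-ups: variance factor (1 + 2 × 0.45)/3 = 0.633. Then 233.5 × 0.633 × 3/0.65 = 683.
- The same, adjusted for baseline: factor 0.633 − 0.45² = 0.431. Then 233.5 × 0.431 × 3/0.65 = 464, and 582/464 = 1.25.

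The stated N may therefore contain an inflation for interactions, but its size cannot be recovered.

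**2. Information kept after a split.** For a normal score cut so that a proportion p lies on one side, with linear moderation, efficiency relative to the score is φ(z_p)²/[p(1 − p)]. If the score test has 0.90 power, the split test has power Φ[(1.96 + 1.2816)√efficiency − 1.96].

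| Split | φ(z_p) | Efficiency | Loss | Power after split |
|---|---|---|---|---|
| 50/50 | 0.399 | 0.637 | 36.3% | 0.73 |
| 30/70 | 0.348 | 0.576 | 42.4% | 0.69 |
| 20/80 | 0.280 | 0.490 | 51.0% | 0.62 |
| 10/90 | 0.175 | 0.342 | 65.8% | 0.47 |

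The median split is the best case for a normal score.

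**3. On this trial's scale.** 582 × 0.65 = 378, or 126 per arm. Assume that the format effect differs by 0.5 SD between the two subgroups; this size is not in the documents. For one two-arm contrast with outcome variance factor v:

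- Split: SE = √[2v/(n p(1 − p))].
- Score: the effect per SD of score is 0.5/gap, where gap = φ(z_p)/[p(1 − p)] is the mean score difference between the subgroups; SE = √(2v/n).

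At one time point (v = 1) and a 50/50 split, the split test has SE √(2/31.5) = 0.252 and power Φ(0.5/0.252 − 1.96) = 0.51. On the score, gap = 1.596, the effect is 0.313 and SE is 0.126, so power is Φ(0.313/0.126 − 1.96) = 0.70.

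| Case | Split | Power, split | Power, score |
|---|---|---|---|
| One time point (v = 1) | 50/50 | 51% | 70% |
| One time point (v = 1) | 20/80 | 36% | 62% |
| Mean of three follow-ups, baseline-adjusted (v = 0.431) | 50/50 | 86% | 97% |
| Mean of three follow-ups, baseline-adjusted (v = 0.431) | 20/80 | 68% | 93% |

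Simulation of the one-time-point case (3,000 runs per split) gave 50% against 70%, and 35% against 62%. No figure here is adjusted for multiplicity.

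**The case against.** **The loss is not a fact about this trial.** A reader might infer that 36 to 51% of the information will be lost. The documents give no score distribution, split proportion or form of moderation, so they support only the conditional statement. It does not apply to race or rural/urban residence at all. This part of the objection stands.

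**The moderator analyses are not shown to be weak.** A reader might infer that they are underpowered already. The plan claims 0.90, and the missing ratio means that this cannot be refuted. With 126 per arm and splits from 50/50 to 20/80, power for an interaction of 0.3 SD is 22 to 16% at one time point and 44 to 31% with the baseline-adjusted mean. For 0.6 SD it is 66 to 48% and 95 to 83%. The answer depends on an interaction size that the plan does not state.

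**Nor is a fall from the plan's 0.90 shown.** Because the moderator analyses are described as subgroup contrasts, the stated 0.90 may belong to the split test. Under the same assumptions the score test would then reach Φ(3.2416/√0.637 − 1.96) = 0.98 at 50/50 and Φ(3.2416/√0.490 − 1.96) = 0.996 at 20/80. The relative loss is the same, but the practical gain is smaller.

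**The model might use scores anyway.** The coding of the characteristic is not stated, and no text ties a named instrument to the disability contrast. That stands as a limit on the word *only*. Still, the two-category definition is the only one offered, and if scores are intended, the plan should say so.

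**Subgroups are the stated question, and moderation may have a threshold.** A linear interaction asks a somewhat different question from a subgroup contrast, and a threshold at the cut could favour the split. But the plan names no threshold, and testing on the score does not prevent showing subgroup estimates.

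**Conclusion.** The point holds as a conditional one. For disability and the five psychosocial traits, the plan describes two-category contrasts with no cut-points while listing scored instruments. With a roughly normal score and linear moderation, splits from 50/50 to 20/80 cost about 36 to 51% of the interaction information, equivalent to 0.90 power on the score becoming 0.73 to 0.62. More uneven splits cost more.

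The absent cut-points and the unclear *and/or* can be read directly from the text and need no assumption. The documents do not establish that the moderator analyses are weak or that scores are ruled out. The moderator tests are affected, not the noninferiority comparison of formats.

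**What to change.** - For disability and each psychosocial trait, name the instrument and base the test of group by time by characteristic on its continuous baseline score. Add a simple check for non-linearity, such as a quadratic term.
- State whether the psychosocial traits are tested separately or as one pooled characteristic.
- Report format differences with 95% CIs at prespecified score values, or in subgroups with prespecified cut-points, so that stakeholders still see subgroup results.
- Keep race and rural/urban as categories.
- State the interaction-to-overall effects ratio and the contrast to which the 0.90 refers.

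Cost: a few sentences in the plan and no new data. The change is cheap but not free. It adds a linearity assumption, and entering the five psychosocial traits separately would raise the number of moderators from four to eight (4 − 1 + 5), each with two remote-format comparisons.
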